1.2.2 General Toxicology

Treprostinil diolamine did not demonstrate any carcinogenic effects in mouse or rat carcinogenicity studies. Oral administration of treprostinil diolamine to Tg.rasH2 mice at 0, 5, 10 and 20 mg/kg/day in males and 0, 3, 7.5 and 15 mg/kg/day in females daily for 26 weeks did not significantly increase the incidence of tumors. The exposures obtained at the highest dose levels used in males and females are about 8- and 17-fold, respectively, the human exposure at the mean dose of 3.4 mg BID. Oral administration of treprostinil diolamine to Sprague Dawley rats at 0, 1, 3 and 10 mg/kg/day daily for 104 weeks did not significantly increase the incidence obtained at the highest dose levels used in males and 9.3 mg/kg/day daily for 104 weeks did not significantly increase the incidence of tumors. The exposures obtained at the highest dose levels used in males and 9.3 mg/kg/day daily for 104 weeks did not significantly increase the incidence of tumors. The exposures obtained at the highest dose levels used in males and females are about 25- and 40-fold, respectively, the human exposure at the mean dose of 3.4 mg BID.

In vitro genotoxicity studies with high doses of treprostinil did not demonstrate any mutagenic or clastogenic effects. Treprostinil as the diolamine salt was tested *in vivo* in a rat micronucleus assay and did not induce an increased incidence of micronucleated polychromatic erythrocytes.

No adverse effect doses for fertility, fetal viability/growth, fetal development (teratogenicity), and postnatal development were determined in rats. In pregnant rabbits, external fetal and soft tissue malformations and fetal skeletal malformation occurred with the no observed adverse effect level for these adverse effects of 0.5 mg/kg/day (five times the human exposure).

1.2.3 Clinical Pharmacology

The absolute bioavailability following administration of the oral treprostinil extended release tablet is 17% compared with IV Remodulin. Maximum treprostinil concentrations occur between approximately 4 and 6 hours following administration of oral treprostinil in adults.

Following administration, oral treprostinil is widely distributed. Oral treprostinil is approximately 96% protein bound with no effect on warfarin or digoxin displacement. Pharmacokinetic area under the curve (AUC) data; indicate that Day 1 data are predictive of Day 13 and linearity was observed in plasma exposure comparing 1 mg and 2 mg doses in healthy volunteers. Food, particularly a high calorie meal, has been observed to increase absorption and prolong exposure, contributing to the desired pharmacokinetic profile. The relative bioavailability of treprostinil following oral administration of a 1 mg extended release tablet was not significantly altered by meal types ranging from 250 to 500 calories in healthy adult volunteers.

Treprostinil is primarily metabolized by cytochrome (CYP) 2C8 and to a lesser extent by CYP2C9. It is unknown if the metabolism of oral treprostinil will be altered in pediatric patients. A study evaluating the metabolism of paclitaxel by CYP2C8 using pediatric and adult liver microsomes found no age-related differences in metabolism [Blanco, 2000]; however, CYP2C9 activity appears to be increased in children. Clearance is approximately twice that of adult values for several drugs predominately metabolized by CYP2C9, including warfarin, phenytoin, and celecoxib [Anderson, 2009]. Co-administration of oral treprostinil with a strong CYP2C8 inhibitor (*e.g.*, gemfibrozil) has been demonstrated to result in significant elevation of treprostinil plasma concentrations.

In a study conducted in healthy volunteers using [¹⁴C] treprostinil, 78.6% and 13.4% of the subcutaneous dose was recovered in the urine and feces, respectively, over 10 days. Only 4% was excreted as unchanged treprostinil in the urine. Five metabolites were detected in the urine, ranging from 10.2% to 15.5% and representing 64.4% of the dose administered. Metabolites of treprostinil were tested for pharmacologic activity and found to be much less hemodynamically active than treprostinil itself. Specifically, metabolite M388 was 100- to 1,000-fold less active than treprostinil, metabolites M392 and M566 were 1,000-fold less active than treprostinil, metabolites M392 and M566 were 1,000-fold less active than treprostinil, metabolites M392 and M566 were than treprostinil (i.e., did not affect blood pressure or heart rate at the highest dose tested). Metabolites M348 and M374 likewise had little cardiovascular activity, having some

0.01-0.05% the activity of parent drug. It is concluded that the metabolites contributed very little to pharmacologic activity in this model.

Initial clinical studies used a twice a day dosing regimen; however, a three times a day dosing (TID) regimen has been evaluated and a reduction in the peak-to-trough fluctuations observed. A TID regimen more closely resembles a parental infusion to facilitate the achievement of higher doses with greater clinical effect on the signs and symptoms of PAH, and reduces the occurrence of prostacyclin-related adverse events previously seen with the twice daily regimen. Successful transition of stable adult PAH subjects from parenteral treprostinil (IV or subcutaneous [SC] infusion) to a TID regimen with oral treprostinil without a significant decline in exercise capacity or worsening functional classification has been demonstrated in a recent clinical trial [White, 2014].

1.2.4 Clinical Trials Experience

Oral treprostinil has been administered to over 1,800 subjects in phase I-III trials. Doses of up to 3 mg BID have been administered to healthy volunteers and subjects with PAH have received up to 28 mg TID in phase III and open-label studies. As reported as of February 2014, the average exposure has been approximately two years and the longest exposure reported as almost six years.

Oral treprostinil has been evaluated in studies in subjects with PAH as monotherapy and in combination with endothelin receptor antagonist (ERA) and phosphodiesterase type 5 inhibitor (PDE-5i) therapies.

In a 12-week, randomized (2:1 oral treprostinil to placebo), double-blind, placebo-controlled, international study in subjects with WHO Group 1 PAH not currently receiving PAH therapy, subjects receiving oral treprostinil improved their median 6MWD at Week 12 by approximately +23 meters (Hodges-Lehmann estimate; p=0.013, non-parametric analysis of covariance in accordance with the pre-specified statistical analysis plan in the primary analysis population; n=228) as compared to subjects receiving placebo. The within group median change from baseline was +25 meters for oral treprostinil and -5 meters for placebo at

Week 12 (n=228). Mean dose (\pm SD) in the oral treprostinil group was 2.3 \pm 1.3, 3.2 \pm 1.9, and 3.4 \pm 1.9 mg BID at Weeks 4, 8, and 12, respectively.

The study enrolled 349 subjects (overall analysis population) who were not receiving any PAH medication. Subjects were in WHO functional class II (~33%) and class III (~66%) with either idiopathic or heritable PAH (~75%), collagen vascular disease associated PAH (~19%), or PAH associated with HIV (1%) or congenital heart defect (5%) or other conditions (~6%). The mean baseline 6MWD was approximately 330 meters.

Subjects were administered oral treprostinil or placebo twice daily, with the doses titrated to effect up to a maximum of 12 mg BID based on clinical response and study drug tolerability. At the beginning of the study, subjects were dosed with only the 1 mg tablets, with 0.5 and 0.25 mg tablets introduced at sequentially later dates during the study. The primary analysis population consisted of the 228 subjects who had access to the 0.25 mg tablet at the time of randomization. Discontinuations occurred in 17% of subjects receiving oral treprostinil compared to 14% of subjects on placebo in this population.

Two 16-week, randomized, double-blind, placebo-controlled, international efficacy and safety studies of oral treprostinil in subjects with WHO Group 1 PAH already receiving treatment with an ERA, PDE-5i or a combination of both have been conducted. The results did not demonstrate a benefit in exercise testing with median 6MWD at Week 16 (11 meters [Hodges-Lehmann estimate; p=0.072] and 10 meters [Hodges-Lehmann estimate; p=0.089], respectively). Subjects were in WHO functional classification II (~23%) and III (~77%) with either idiopathic or heritable PAH (~66%), collagen vascular disease associated PAH (~29%), or PAH associated with HIV (1%) or congenital heart defect (4%). The mean baseline 6MWD was approximately 340 meters. Approximately 40% of enrolled subjects were receiving both an ERA and a PDE-5i.

Over 824 subjects have received oral treprostinil in a long-term, uncontrolled, open-label ongoing extension study. About 70% of subjects continued treatment with oral treprostinil for at least a year. The mean dose was 4.2 mg BID at one year. The dose of oral treprostinil continued to increase over time with doses (mean \pm SD) of 3.6 \pm 2.7, 4.1 \pm 3.1, and 5 \pm 3.7 mg

BID at 6 (n=649), 12 (n=433), and 24 months (n=238), respectively. In the 522 subjects that completed the 12-month efficacy assessment, their mean 6MWD improved by 24 meters compared to baseline (30 meters in subjects not on another PAH therapy and 20 meters when oral treprostinil was used in combination with an ERA and/or a PDE-5i). Of the subjects that remained in the study, overall survival was 92%, 87%, and 82% at the end of 1, 2, and 3-years, respectively, with progression-free survival (progression defined as death, discontinuation or addition of a PAH therapy) of 74%, 61%, and 47%. Reasons for discontinuation from the study included adverse event (16%), progression of disease (15%), death (13%), and withdrawn consent (7%).

The most frequent adverse events (AEs) associated with oral treprostinil that occurred more frequently than placebo in clinical trials were related to systemic effects that are characteristic of prostacyclin (*e.g.*, headache, diarrhea, nausea, flushing, pain in jaw, pain in extremity).

A comprehensive description of oral treprostinil, including the pharmacology, toxicology, and clinical studies completed to date may be found in the Orenitram Package Insert and current version of the Investigators' Brochure.

1.3 RATIONALE FOR DEVELOPMENT OF STUDY DRUG IN DISEASE/CONDITION

Parenteral prostacyclins are considered by many providers as the "gold standard" treatment for PAH. Currently, the complexity and risks associated with approved prostanoid therapy including line sepsis, thromboembolism, and rebound hypertensive crisis limit its utility in clinical practice, particularly in children [Melnick, 2010]. Because of the risks and limitations of continuous parenteral infusion, an alternative route of administration would be desirable for adults as well as children.

Oral treprostinil is a prostacyclin analogue, a class of medication that has long played a prominent role in the treatment of PAH [Badesch, 2004]. Prostacyclin, an endogenous compound produced by the vascular endothelium, has several activities that are relevant to the treatment of pulmonary arterial hypertension. The similarity between adults and children with PAH in underlying pathobiological mechanisms supports the extrapolation that medicinal

products that are effective in adults would also be effective in children. In addition to the data in adult patients establishing the safety and efficacy and supporting the regulatory approval of parenteral prostacyclin and prostacyclin analogue products, it has been reported that the use of IV epoprostenol in children is associated with clinical benefit and improved survival [Barst, 1999; Yung, 2004]. In a recent observational study evaluating the efficacy and tolerability of SC treprostinil for refractory pediatric pulmonary hypertension, eight children aged from 15 months to 10 years old received SC treprostinil therapy at doses ranging from 37-60 ng/kg/min. Of the eight children treated, seven showed improvement in functional classification, hemodynamic, and/or 6MWD (p<0.05), suggesting treprostinil is effective in children with pulmonary hypertension [Levy, 2011]. Additionally, a study in 13 children aged 3-17 years with PAH suggested that IV treprostinil is a therapeutic alternative to IV epoprostenol, with fewer side effects [Ivy, 2007]. Successful transitions from IV to oral or inhaled therapies (PDE-5i, ERA, calcium channel blockers, inhaled iloprost) have been previously demonstrated in studies in children aged six years or greater [Ivy, 2004; Melnick, 2010]. A retrospective study of 77 pediatric PAH patients receiving epoprostenol (n=37), treprostinil (n=20), or were transitioned from epoprostenol to treprostinil (n=20), reported a 5-year transplant-free survival of 70% (95% confidence interval, 56%-80%). Hemodynamic changes over time on treprostinil were similar to epoprostenol. There was a significant improvement in the pulmonary-to-systemic vascular resistance ratio with treprostinil after 2 years of therapy and a trend toward improvement on epoprostenol after 1 to 2 years of therapy; although, these changes were not sustained over the 4 year follow-up period [Siehr, 2013].

Given the established beneficial effects of prostanoid therapy in PAH and the limitations of existing prostanoid medications, oral treprostinil may provide therapeutic benefit to pediatric patients with PAH who are old enough to safely take the medication.

1.4 CLINICAL HYPOTHESIS

This study aims to test the safety and tolerability of oral treprostinil in three cohorts of pediatric subjects aged 7 to 17 years: transitioning from IV/SC Remodulin, transitioning from inhaled prostacyclin, and as add-on to current PAH therapy in de novo prostacyclin subjects.

The hypothesis of this study is that stable PAH pediatric subjects can be safely be transitioned from IV/SC Remodulin to oral treprostinil therapy while maintaining the clinical benefit of the infused therapy. A recent study in stable, carefully-selected PAH adult subjects receiving IV/SC Remodulin demonstrated that subjects can be safely transitioned to oral treprostinil three times daily (TID) dosing under close medical observation without a significant decline in exercise capacity or worsening functional classification [White, 2014]. After analysis of interim pharmacokinetic data from this study, it was determined that a four times daily (QID) dosing regimen in select pediatric subjects may achieve a better pharmacokinetic profile than a TID regimen, potentially providing a clinical benefit. Additionally, we hypothesize that initiation of oral treprostinil in pediatric subjects following transition from inhaled prostacyclin or added to current PAH therapies in de novo prostacyclin subjects will result in clinical improvement compared to Baseline.

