## 8.2 MULTIPLE COMPARISONS AND MULTIPLICITY

No adjustment for multiple comparisons will be made in these analyses, as no formal hypotheses are being tested.

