### 10.2 CARDIOPULMONARY EXERCISE TESTING

Cardiopulmonary exercise testing will be completed at Baseline and Week 24 or premature termination. Exercise data will be sent to a central site and analyzed by a centralized specialist. Cardiopulmonary exercise testing entails measurements of oxygen uptake (VO2), carbon dioxide output (VCO2), minute ventilation (VE), and other variables.

The listing of CPET will include the scheduled visit; date/time of assessment; Remodulin, oral treprostinil, Tyvaso, and Ventavis dosing information prior to the CPET assessment, as

applicable; as well as baseline (pre-exercise) and exercise (post-exercise) peak VO2, post-exercise peak watts and VE/VCO2 slope, warm-up duration (minutes), exercise duration (minutes), and reason for test termination.

A summary of CPET will be produced for data collected before the exercise (labelled "baseline" on the CRF) and after the exercise (labelled "exercise" on the CRF), separately. The summary of CPET before exercise will include descriptive statistics for VO2 at Baseline and Week 24 by cohort. The summary of CPET after exercise will include descriptive statistics at Baseline and Week 24 for warm-up duration (minutes), exercise duration (minutes), peak VO2, VE/VCO2 slope, and peak watts. Changes from Baseline to Week 24 in peak VO2, VE/VCO2 slope, and peak watts will also be descriptively summarized. These changes will be compared within cohorts using a paired t-test and p-values will be calculated for descriptive purposes; no formal hypothesis testing is planned. The number (percentage) of subjects reporting reasons for test termination will be summarized categorically (fatigue vs. other) by cohort.

The dosing information prior to testing (number [percentage] of subjects taking each medication type and last dose) will also be summarized by cohort using descriptive statistics.

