### 10.3 SIX-MINUTE WALK TEST

The 6MWT is performed at Screening (optional), Baseline, Week 0 (Cohort 1 only), Week 3, Week 6, Week 12, and Week 24 or premature termination. At each of these visits, 6MWT recovery monitoring (heart rate and oxygen saturation measurements) will occur immediately prior to walk, immediately upon stopping the walk, 1 minute post walk, 2 minutes post walk, and 3 minutes post walk. The listing of 6MWT will include the assessment date/time; any Remodulin, oral treprostinil, Tyvaso, and Ventavis dosing information prior to the 6MWT assessment, as applicable; as well as whether subject attempted walk test (yes/no), reason not attempted (if applicable), total distance walked, Borg dyspnea score, oxygen receipt, and unusual circumstances. Recovery monitoring data (time point, heart rate, oxygen saturation, and total recovery time [minutes]) will be listed separately.

The summary of 6MWT will include the number (percentage) of subjects who received oxygen during the test and experienced any unusual circumstances during the test for each cohort.

The summary of 6MWD will include descriptive statistics for total distance walked by assessment visit and time point for each cohort. Changes from Baseline to each post-Baseline time point in total distance walked will also be summarized by cohort and compared within cohort using a Wilcoxon signed-rank test. P-values will be calculated for descriptive purposes; no formal hypothesis testing is planned.

As a sensitivity analysis, total walk distance data will be imputed using the LOCF method, regardless of the reason for early termination. The summary based on this imputation will follow the same layout as the no imputation analysis described above, while again using the Wilcoxon signed-rank test for descriptive purposes; no formal hypothesis testing is planned.

The summary of 6MWT recovery monitoring will include descriptive statistics for each cohort of heart rate (bpm) and oxygen saturation (%) at each of the 5 time points of assessment at each visit, as well as descriptive statistics of total recovery time (minutes).

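### Cohort 1 is hypothesised to keep the benefit of infused therapy, but the only inferential statistic the SAP plans for 6MWD and CPET is a descriptive p-value against zero change, which cannot support maintenance

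*Protocol*

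**What the plan says.** Protocol section 1.4 sets two different aims. Children coming off IV/SC Remodulin (Cohort 1) are to be "transitioned from IV/SC Remodulin to oral treprostinil therapy while maintaining the clinical benefit of the infused therapy". For the inhaled-transition and de novo cohorts (Cohorts 2 and 3), the expectation is that treatment "will result in clinical improvement compared to Baseline".

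The SAP analyses all three cohorts alike. Changes in 6MWD at each post-Baseline time point are "summarized by cohort and compared within cohort using a Wilcoxon signed-rank test", and the comparison is repeated with LOCF imputation. For peak VO2, VE/VCO2 slope and peak watts, SAP 10.2 says: "These changes will be compared within cohorts using a paired t-test and p-values will be calculated for descriptive purposes". SAP 10.3 adds: "P-values will be calculated for descriptive purposes; no formal hypothesis testing is planned". SAP 8.2 says: "No adjustment for multiple comparisons will be made in these analyses, as no formal hypotheses are being tested".

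Neither document gives a tolerated loss, or a rule for reading a non-significant result in Cohort 1.

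Protocol 10.6 promises a 95% confidence interval for the arithmetic mean in all summaries of continuous variables. The summary statistics listed in SAP section 8 include no interval, and SAP 10.2 and 10.3 describe none.

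The primary measure (Protocol 10.3.1, SAP 10.1) is the percentage of successful transitions: off the earlier prostacyclin at Week 4 and clinically maintained on oral treprostinil through Week 24.

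**The concern.** A test of zero change suits an improvement hypothesis, because rejecting zero in the right direction supports it. Under a maintenance hypothesis the informative question is how large a loss the data still allow, and a p-value against zero does not answer it. The smaller and noisier the cohort, the more easily p exceeds 0.05, whatever happened to the children.

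The protocol's own background shows how such a result could be read. Section 1.4 says the adult switch study demonstrated safe transition "without a significant decline in exercise capacity or worsening functional classification", and section 1.2.3 describes that result in much the same terms. Both present the absence of a significant decline as part of a demonstration. By contrast, section 1.2.4 treats non-significant results in two adult add-on studies (p=0.072 and p=0.089) as not having shown a benefit. A Cohort 1 p-value above 0.05 would fit the first pattern, and could support a claim about exercise capacity that the data do not bear.

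**Working it through.** **Inputs from the documents.** Planned size is 10 to 15 per cohort (Protocol 10.2, SAP section 6). The number in Cohort 1 alone is not fixed: Protocol 3.5 gives about 25 across Cohorts 1 and 2. The total of 40 is 25 + 15, chosen for feasibility, so there is no power calculation to reproduce.

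**Assumptions.** The documents give no SD of 6MWD change, so 50, 60 and 75 m are used. They give no significance level or sidedness, so two-sided 0.05 is used. Changes are taken as normal. True losses of 25, 40 and 60 m are for scale only. The 25 m equals the within-group adult median gain on oral treprostinil in Protocol 1.2.4; it is not an estimate of the benefit of the infusion in children.

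**Step 1: how often a real loss gives p>0.05.** Wilcoxon signed-rank test by simulation, with exact critical values:

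| True loss | n | SD 50 m | SD 60 m | SD 75 m |
|---|---|---|---|---|
| 25 m | 10 | 72% | 79% | 85% |
| 25 m | 12 | 69% | 77% | 84% |
| 25 m | 15 | 58% | 69% | 79% |
| 40 m | 10 | 40% | 55% | 69% |
| 40 m | 12 | 33% | 48% | 64% |
| 40 m | 15 | 20% | 35% | 54% |

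For a 60 m loss, p>0.05 occurs in about 10-41% of trials at n=10 and 1-20% at n=15 over the same SDs. With a wider SD range of 40 to 80 m, a 23 m loss (the adult placebo-adjusted effect in Protocol 1.2.4) gives p>0.05 in 48-87% of trials.

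**Step 2: CPET.** The paired t-test reaches 80% power only when the true mean change is 1.00 SD at n=10, 0.89 SD at n=12 and 0.78 SD at n=15. CPET may be waived below 130 cm (Protocol 3.3.1.1), so its n may be smaller.

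**Step 3: what an interval would show.** The half-width of the 95% interval for a mean change is t(0.975, n-1) x SD / sqrt(n).

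- n=15, SD 50 m: 2.145 x 50 / 3.873 = 27.7 m.
- n=12, SD 60 m: 2.201 x 60 / 3.464 = 38.1 m.
- n=10, SD 75 m: 2.262 x 75 / 3.162 = 53.7 m.

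For illustration, take an observed mean change of -15 m with n=12 and a sample SD of 60 m. The limits are -15 - 38.1 = -53.1 m and -15 + 38.1 = +23.1 m. Zero lies inside, so a t-test gives p>0.05, yet a mean loss of about 53 m is not excluded. The p-value hides this and the interval shows it.

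**The case against.** The strongest reply is that the plan does not use these p-values to decide anything. They are labelled descriptive, no formal hypothesis is tested, the protocol synopsis says the study is not powered, and the transition is judged on the success percentage. All of that stands. A reader might infer that the plan will declare benefit maintained when p>0.05. The documents do not support that: no passage makes it a criterion, and the adult wording describes a cited study, not a success rule for this one.

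A reader might also infer that a lost benefit would go unnoticed. That goes too far as well. The SAP summarises change from Baseline in 6MWD and CPET, daily Week 0 walks in Cohort 1, symptom and functional-class shifts, and NT-proBNP. A loss near 60 m would usually reach p<0.05. The documents do not quantify the infusion's benefit in children, so no figure here can be called its complete loss.

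What remains is narrower. The descriptive label does not change the value that the p-value is computed against. The success percentage depends on being clinically maintained, which neither document ties to any 6MWD or CPET value, so it does not answer the exercise part of the hypothesis. The protocol's interval would answer it better, and the SAP does not carry it over.

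**Conclusion.** The point holds as a mismatch between hypothesis and statistic. For Cohort 1, a p-value against zero change in 6MWD or CPET cannot support maintenance. At the planned size a moderate loss often gives p>0.05: about 58-85% of trials for 25 m and 20-69% for 40 m. These figures rest on the assumed SDs of 50 to 75 m, a two-sided 0.05 level, normal changes and 10 to 15 children with paired data; dropout would make non-significance more likely.

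The consequence is a risk of misreading in the report, not a faulty decision rule. It concerns only the two assessments for which the SAP plans tests, and it does not touch the primary measure. Nor do the documents oblige the sponsor to adopt a non-inferiority margin with a formal decision: the study is descriptive, and neither document supplies a margin.

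**What to change.** In SAP 10.2 and 10.3, for Cohort 1:

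- Report the change from Baseline in 6MWD (mean or Hodges-Lehmann estimate) and in peak VO2, VE/VCO2 slope and peak watts, each with 95% confidence limits. This restores the kind of interval promised in Protocol 10.6.
- Base any statement about maintained exercise capacity on the limit in the direction of worsening (for 6MWD, the lower limit).
- State that p>0.05 is not evidence of maintenance, and either omit the Cohort 1 p-values or label them so.

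The tests for Cohorts 2 and 3 can stay, since their hypothesis is improvement. A tolerated loss set before database lock is optional and for the sponsor to justify. As a strict rule it would rarely be met: with no true loss and an illustrative 25 m margin, a t-based approximation at SD 50 to 75 m excludes that loss in only 16-29% of trials at n=10 and 22-44% at n=15.

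The cost is SAP wording and a changed table column, with no new data or visits. The downside is a wide interval, about 28 to 54 m either side for 6MWD, so the Cohort 1 result will look less favourable than a bare non-significant p-value.
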